9.1.2. Self-controlled Risk Interval (SCRI) Design

[figure not shown]
A SCRI design will be used for a subset of study outcomes that meet the necessary study design assumptions, as a complementary analytic approach. The assumptions for a SCRI design include that the outcome must have acute onset and short latency, as well as a relatively well-defined risk interval. The assumptions underpinning the SCRI also require that occurrence of the outcome does not affect the probability of exposure. Table 1 in Section 9.3 indicates outcomes for which a SCRI analysis is deemed a valid approach.

The SCRI design uses information from cases (i.e, vaccinated individuals who experience an outcome) to compare the incidence of an outcome in the risk interval following vaccination to the incidence in a post-vaccination control interval within the same individual.^{22, 23}

Unlike the comparative cohort design, which may suffer from potential vaccine exposure under-ascertainment and misclassification as well as potential residual confounding, the SCRI design is a within person analysis that implicitly controls for time invariant confounders. Time varying confounders still need to be controlled for but with short, defined risk windows, the risk of time varying confounding is limited.

Risk intervals will be applied starting on the day after vaccination (Day 1), for a duration of time specific to each outcome; Table 1 in Section 9.3 defines the risk interval proposed for each outcome. A prespecified post-vaccination control interval will be used for each outcome of interest. The post-vaccination control interval will occur after the risk interval associated with ABRYSVO administration to avoid potential differential reporting of outcome in the pre- and post-vaccination periods. The risk and control intervals are based on a review of the published literature and precedence from previous studies of vaccine safety (see Table 1). As an example, the SCRI design with 42-day risk interval and 42-day post-vaccination control interval for Guillain-Barré syndrome (GBS) is presented in Figure 3 below.

Figure 3 Self-controlled Risk Interval Design

PFIZER CONFIDENTIAL CT24-WI-GL02-RF02 5.0 Non-Interventional Study Protocol Template For Secondary Data Collection Study 01-Aug-2023 Page 23 of 72

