9.3.1.2. SCRI Design

For the SCRI design, person-time in the risk interval will be considered "exposed," while person-time in the control interval will be considered "unexposed." Risk intervals will be specific to the outcome of interest and are defined to reflect the

duration of time post-vaccine exposure that an incident post-vaccine event is expected to occur based on biological plausibility. Events known to have a risk window limited to a defined period after vaccination are not well known for ABRYSVO and other RSV vaccines, therefore event-specific intervals will be defined based on prior post-marketing studies of other vaccines (where applicable), clinical trial data (where applicable), and passive post-marketing surveillance activities (as they become available).

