9.7.4. Sensitivity Analyses

As feasible, sensitivity analyses, as well as analyses to evaluate potential bias, may include, but are not necessarily limited to:

- Comparative cohort design with extended risk windows for the acute outcomes to assess potential outcome under-reporting and misclassification
 - The exception will be atrial fibrillation and supraventricular arrhythmias where shorter risk windows of 0-3 days (as well as 0-1 days and 0-30 days) will be considered to allow for greater consistency with the ongoing ABRYSVO safety study in the Veterans Affairs population (C3671037). Further details on alternative risk intervals will be provided in the SAP.
- SCRI with alternative risk and control intervals to assess potential exposure misclassification. In addition, to allow for greater consistency across ongoing ABRYSVO vaccine safety studies, specifically C3671031 and C3671037, the following risk intervals will be applied as sensitivity analyses for the following AESIs:
 - GBS: risk interval 1-21 days⁵⁹
 - Acute disseminated encephalomyelitis: risk interval 5-28 days ⁶⁰
 - Transverse myelitis: risk interval 1-21 days ^{59, 61}

PFIZER CONFIDENTIAL

CT24-WI-GL02-RF02 5.0 Non-Interventional Study Protocol Template For Secondary Data Collection Study 01-Aug-2023 Page 48 of 72

- A SCRI analysis may also be considered for atrial fibrillation and supraventricular arrhythmias with risk intervals of 0-3 days, 0-1 days and 0-30 days to align with the planned SCRI analysis from study C3671037. Further details on alternative risk and control intervals will be provided in the SAP.
- SCRI with pre-vaccination control interval. If vaccination is deferred while unwell with symptoms related to outcomes, this may violate the assumption of the SCRI design that an outcome event should not alter the probability of subsequent exposure to vaccination. Defining a separate pre-vaccination window can assess these design assumptions and ensure that they are not violated.
- SCRI with a washout period between risk and control intervals, within the subset of outcomes for which an increased risk is detected
- For outcomes with CFR >20%, SCRI analysis incorporating Farrington adjustment or extending follow-up after death for full length of risk and control window
- Use of narrow and broader definition algorithms for outcomes to assess outcome misclassification (comparative cohort and SCRI)

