A limitation common to both the comparative cohort and SCRI designs is that any uncertainty regarding risk periods may lead to misclassification and attenuation of risk estimates. However, this will be minimized by using risk intervals based on prior evidence of biological plausibility. The potential for misclassification of the risk period will also be investigated by varying risk intervals within sensitivity analyses.

Administration of other vaccines during follow-up is a potential time varying confounder. Similarly, receipt of other vaccine shortly before the index date may confound the observed outcome risks. The potential for time varying confounding will be assessed by descriptively evaluating whether there is differential receipt of other vaccines during follow-up between the vaccinated and unvaccinated cohorts within the comparative cohort design, as well as between the risk and post-vaccination control intervals for the SCRI design. If the distribution of non-ABRYSVO vaccine administration is imbalanced, additional analyses will be conducted to account for this imbalance. These may include censoring follow-up at receipt of additional vaccines in the comparative cohort design and stratifying analyses by receipt of additional vaccines for the SCRI design. To explore the residual effects of

PFIZER CONFIDENTIAL

CT24-WI-GL02-RF02 5.0 Non-Interventional Study Protocol Template For Secondary Data Collection Study 01-Aug-2023 Page 54 of 72 vaccination receipt prior to index, sensitivity analyses can be considered excluding individuals with prior receipt of vaccines within a pre-specified time window (e.g., 30 or 45 days prior to index).

Finally, a limitation of the cohort design is the potential for residual confounding from unmeasured confounders. Potential confounders will be accounted for in the statistical analysis using ATT weighting to achieve balance and adjustment for known confounders between cohorts. However, unmeasured confounding may remain due to variables not being captured within the routine healthcare datasets or being subject to missingness. As feasible, the potential for residual confounding will be explored in several ways: The within-person SCRI design will also be applied where appropriate which accounts for time invariant confounding, and additional sensitivity analyses including negative controls will be considered to further quantify the potential for residual confounding.

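### The SCRI washout analysis is limited to outcomes with a detected increase, so it is least likely to run where carry-over into the control interval is strongest

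*Protocol*

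**What the plan says.** The SCRI is a complementary design to the primary comparative cohort and is applied to the outcomes marked Cohort/SCRI in Table 1. On the position of its control interval, Section 9.1.2 states: "The post-vaccination control interval will occur after the risk interval associated with ABRYSVO administration". No gap is described. The worked GBS example in that section uses 42 days for each interval.

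The protocol is open about how uncertain the windows are. Section 9.3.1.2 says: "Events known to have a risk window limited to a defined period after vaccination are not well known for ABRYSVO and other RSV vaccines". Section 9.9 gives the consequence: "any uncertainty regarding risk periods may lead to misclassification and attenuation of risk estimates".

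Section 9.7.4 lists the sensitivity analyses. It opens by saying that "sensitivity analyses, as well as analyses to evaluate potential bias, may include, but are not necessarily limited to" the items that follow. The washout item is "SCRI with a washout period between risk and control intervals, within the subset of outcomes for which an increased risk is detected". The text does not say which analysis must detect the increase. Two other SCRI items carry no such condition: "SCRI with alternative risk and control intervals to assess potential exposure misclassification" and "SCRI with pre-vaccination control interval". Nor does the cohort analysis with extended risk windows for acute outcomes.

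**The concern.** A washout between the risk and control intervals protects the control interval from excess events that arise after the assumed risk window has closed. Such events raise the control-interval rate and push an IRR above 1 down towards 1. The typical symptom of carry-over is thus a weakened or null SCRI result.

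The condition asks for a raised result before the washout is done. Used that way, the washout can revise an estimate already found to be raised, but it cannot question a null. In a safety study the missed signal is the costly error, and here the protocol itself names both the uncertainty about the windows and the direction of the bias.

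**Working it through.** **The plan's own figures.** The protocol gives no sample size or power for the SCRI. Table 2 covers the cohort design only. Its GBS entry (6 per 100,000 person-years, 42-day risk 0.0000069, IRR 2, two-sided alpha 0.05, power 80%) reproduces: (1.960 + 0.842)² × (1 + 2) / 0.0000069 = 3,412,557 per cohort. This does not bear on the washout question.

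**Inputs to the illustration.** The 42-day intervals come from the GBS example in Section 9.1.2. Assumed, because the protocol gives none: tail length and height, 20 expected baseline events per interval, a control interval that starts straight after the risk interval, and detection meaning a two-sided 0.05 Wald test on the log IRR in the main SCRI.

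**Effect on the IRR.** With true rate ratio r in the risk interval, and d days of the control interval at rate ratio t:

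expected IRR = r / [(d × t + 42 − d) / 42]

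- r = 2, d = 14, t = 1.5: 2 / (49/42) = 1.71
- r = 2, d = 14, t = 2: 2 / (56/42) = 1.50
- r = 3, d = 14, t = 2: 3 / (56/42) = 2.25

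**Effect on detection.** Risk-interval events are Poisson with mean 20 × r. Control-interval events are Poisson with mean 20 × the bracketed term. Summing over both counts for r = 2:

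| Control interval | Expected IRR | Power | Loss due to carry-over |
|---|---|---|---|
| No carry-over | 2.00 | 73.5% | none |
| 14-day tail at 1.5 | 1.71 | 54.9% | 18.6 points |
| 14-day tail at 2 | 1.50 | 36.5% | 37.1 points |

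**Second calculation, other assumptions.** This uses an exact conditional binomial test, 24 expected baseline events per interval (72 in all at IRR 2 without carry-over), and a tail at the full IRR of 2:

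| Days of carry-over | 0 | 7 | 14 | 21 | 28 | 42 |
|---|---|---|---|---|---|---|
| Expected IRR | 2.00 | 1.71 | 1.50 | 1.33 | 1.20 | 1.00 |
| Chance of detecting an increase | 79% | 59% | 39% | 22% | 11% | 2% |

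If detection must come from the main SCRI, the last row is also the chance that the washout is run. It falls steadily as carry-over lengthens.

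**What a washout restores (r = 2, tail at 2).** With 14 days of carry-over, a 14-day gap moves the expected IRR from 1.50 to 2.00. With 21 days, a 14-day gap leaves 7 contaminated days and gives 2 / (1 + 7/42) = 1.71; a 21-day gap gives 2.00.

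**The case against.** The case against giving this much weight is substantial.

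- **The SCRI is not the only look.** Every SCRI outcome in Table 1 is also analysed in the primary cohort. Its comparators are unvaccinated and are censored at RSV vaccination, so a late tail among the vaccinated cannot contaminate the comparator rate. A reader might infer that outcomes masked by carry-over are bound to be reported as null. The documents do not support that.
- **The trigger is ambiguous.** The clause does not require the increase to be detected by the SCRI. If a cohort signal counts, an outcome with a null SCRI could still receive the washout. A reader might infer that such an outcome can never reach it; the text does not go that far. The ambiguity does need settling, and both designs can be null.
- **Other checks carry no trigger.** Extended cohort windows, alternative SCRI intervals and a pre-vaccination control are all listed unconditionally, and Section 9.9 promises to vary the risk intervals. This covers part of the gap. However, the alternative risk intervals named for GBS, acute disseminated encephalomyelitis and transverse myelitis all end before day 42. If the control interval then starts straight afterwards, carry-over could worsen. The pre-vaccination control is offered to test deferral of vaccination, and it brings back the pre/post reporting difference that Section 9.1.2 gives as the reason for a post-vaccination control. None of these analyses is stated to address carry-over into the control interval.
- **The list is optional and open.** The SAP may add analyses. That lowers the severity, but the protocol still states a selection rule, and the rule points the wrong way.
- **The numbers are assumed.** At the protocol's GBS risk, 20 baseline events need 20 / 0.0000069, or about 2.9 million vaccinated people. The alpha and the excess-risk threshold are left to the SAP. Adjacency of the intervals is inferred from the absence of a stated gap, since Figure 3 is not shown.

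**Conclusion.** The point stands as a moderate one: the trigger is badly chosen for its purpose. It makes the washout less likely to run as carry-over grows, and it prevents the washout from testing a null SCRI result unless another analysis counts as detection. The direction does not depend on the assumed values; the size does.

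Under the first set of assumptions, a true IRR of 2 with a 14-day tail reads 1.50 to 1.71, and 18.6 to 37.1 points of power are lost to carry-over. A reader might instead take the whole non-detection rate (45.1% to 63.5%) as the price of the trigger. That overstates it, because 26.5 points would be missed with no carry-over at all, and because cohort detection is ignored. The cohort analysis and the untriggered checks reduce the gap without closing it.

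**What to change.** In Section 9.7.4, delete the condition on a detected increase. State that the SCRI with a washout will be run for every Cohort/SCRI outcome in Table 1, whatever the main result, with the gap length fixed in advance for each outcome. Report the result beside the main SCRI IRR. The question of which design must detect the increase then no longer arises.

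The edit is one clause, plus further runs of an analysis already planned. The real cost is a longer required observation span: with 42-day intervals and an assumed 14-day gap, 42 + 14 + 42 = 98 days instead of 84. Some more cases will be excluded under the full-accrual rule in Section 9.2.1, including through death, which Section 9.7.3.2 already raises. The wider span also leaves slightly more room for time-varying confounding. Both are acceptable in a sensitivity analysis and should be mentioned when its result is read.

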9.7.3.2. SCRI Design

SCRI design with post-vaccination control interval will compare the incidence of prespecified outcomes occurring in the risk interval following ABRYSVO vaccination with the incidence of prespecified AESIs occurring during the post-vaccination control interval.

In order to account for the self-matched design, a conditional Poisson regression model will be used to estimate relative incidence and 95% CIs. The dependent variable will be the

number of events occurring during the risk or control window. The independent variables in all the models will be the type of window (risk or control), and the person-time in each considered window, which will be handled as an offset term. The SCRI inherently adjusts for both measured and unmeasured time constant factors such as sex and chronic health conditions with onset before the start of follow-up. Time-varying confounders may be included as covariates in regression models. Outcomes for which the SCRI design will be a complementary design, and corresponding risk windows for such outcomes are described in Table 1.

As noted in Section 9.2.1, individuals in the SCRI design will be required to have full accrual of data to define the outcome in the risk and control intervals combined. If an outcome of interest (e.g., cardiac outcome) substantially increases the mortality risk, death may prevent individuals from accruing the full follow-up period, leading to their exclusion from the SCRI study. To evaluate this possibility, the 30-day CFR will be calculated for each outcome. Outcomes with a high 30-day CFR (e.g., >20%) will be considered for further adjustment in the SCRI design. Approaches may include using the Farrington adjustment as the primary analysis or extending follow-up periods to include individuals who die following an outcome of interest in the SCRI analyses. The final 30-day CFR threshold, and details of the adjustment method, will be specified in the SAP.

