- Descriptive analyses will be conducted to assess whether there is differential receipt of other vaccines in the follow up period between the vaccinated and unvaccinated cohort (comparative cohort design) and between the risk and control intervals (SCRI design). Differential receipt of vaccines during follow up may introduce potential time varying confounding. If differential patterns of vaccination during follow up are observed, the following approaches may be considered:
 - Comparative cohort analysis with censoring at receipt of another vaccine during follow-up
 - SCRI with analyses stratified by those who did and did not receive vaccinations during the risk or control interval
 - For individuals with receipt of other vaccines close to index (e.g.,30 or 45 days prior to index), comparative cohort and SCRI analyses will be repeated excluding those individuals
- Quantitative bias analysis to assess potential unmeasured confounding (comparative cohort)
- Negative control outcome analyses will be considered to assess potential unmeasured confounding, selection bias, and misclassification bias (for both comparative cohort and SCRI designs). As different AESIs may be associated with different care and medical encounter patterns reflecting different bias structures, careful consideration should be given to which negative controls are appropriate for which AESI analyses. As such, several negative controls may be considered for inclusion, including, but not limited to, accidental poisoning, appendicitis, cataracts, or non-vertebral fractures. Further details on the choice of negative control outcomes will be described in the SAP.

Further details and any additional sensitivity analyses that may be conducted will be described in the SAP.

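### Stratifying the SCRI by other vaccines received in the risk or control interval splits cases on a status the event can change, and leaves the other vaccine's timing uncontrolled

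*Protocol*

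**What the plan says.** Protocol 9.7.4 plans a descriptive check of whether other vaccines are received unevenly between the SCRI risk and control intervals. The consequence is worded permissively: "If differential patterns of vaccination during follow up are observed, the following approaches may be considered". The SCRI option for vaccines given during follow-up is "SCRI with analyses stratified by those who did and did not receive vaccinations during the risk or control interval". Section 9.9 repeats it as a possible remedy: "stratifying analyses by receipt of additional vaccines for the SCRI design". Neither section limits the stratifying variable to vaccines given before the event or before index.

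Three other statements bear on this:

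- Section 9.1.2 says the SCRI assumptions "require that occurrence of the outcome does not affect the probability of exposure". Section 9.7.4 returns to this for the study vaccine: "If vaccination is deferred while unwell with symptoms related to outcomes, this may violate the assumption of the SCRI design".
- For outcomes with a case fatality above 20%, one option in 9.7.4 is "extending follow-up after death for full length of risk and control window".
- Section 9.7.3.2 already allows another route: "Time-varying confounders may be included as covariates in regression models".

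The 30/45-day pre-index exclusion appears in 9.7.4 beneath the follow-up-imbalance condition. Section 9.9 offers it without that condition.

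**The concern.** Receipt at any time in the risk-plus-control window is a post-index variable. Someone with a serious event on day 10 has most of the window left in which a planned influenza or COVID-19 vaccine could be dropped; someone whose event falls on day 80 has almost none. If events reduce later vaccination, risk-interval cases move from the receiver stratum to the non-receiver stratum more often than control-interval cases do. For cases who die but are kept for the full window, no assumption about behaviour is needed, since they cannot be vaccinated later.

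The split also does not do its job among receivers. It records that another vaccine was given but not when, so any effect of that vaccine still falls unevenly on the two intervals.

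At stake is how a fallback safety analysis is read: ABRYSVO could appear protective when another vaccine follows and mildly harmful when given alone, with neither being true.

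**Working it through.** The protocol attaches no figure to this point, so there is nothing to reproduce first.

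**Inputs.** Risk and control intervals of 42 days each come from the Guillain-Barré example in 9.1.2, giving a window T = 84 days. The rest is assumed, because the protocol gives none of it: true IRR of 1 with event times uniform over the window; another vaccine planned for p = 40%, uniformly over the window; and c, the fraction of vaccines due after the event that are cancelled.

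**Step 1: strata under the null.** For an event at time t, the probability of being a receiver is p[1 − c(1 − t/T)]. The mean of t/T is 0.25 in the risk interval and 0.75 in the control interval. With equal intervals the stratum IRR is risk-interval cases over control-interval cases:

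- Receivers: (1 − 0.75c) / (1 − 0.25c)
- Non-receivers: [1 − p(1 − 0.75c)] / [1 − p(1 − 0.25c)]

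| c | Receivers | Non-receivers | All cases |
|---|---|---|---|
| 0 | 1.00 | 1.00 | 1.00 |
| 0.25 | 0.8125/0.9375 = 0.87 | 0.675/0.625 = 1.08 | 1.00 |
| 0.50 | 0.625/0.875 = 0.71 | 0.75/0.65 = 1.15 | 1.00 |
| 1.00 | 0.25/0.75 = 0.33 | 0.90/0.70 = 1.29 | 1.00 |

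Simulation agrees with these values.

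**Step 2: a different vaccination model.** Take a constant hazard giving a 30% chance of another vaccine over 84 days without an event, changed after an event. Receivers / non-receivers:

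- hazard unchanged: 1.00 / 1.00
- hazard halved: 0.75 / 1.09
- no later vaccine: 0.36 / 1.20
- full deferral for 14 days only: 0.97 / 1.01
- full deferral for 28 days only: 0.88 / 1.04
- hazard raised by half: 1.17 / 0.92

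**Step 3: no deferral, but the other vaccine doubles risk for 42 days.** ABRYSVO still has no effect.

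- Given uniformly over 84 days: the mean number of doubled-risk days is 882/84 = 10.5 in the risk interval and 1,764/84 = 21 in the control interval. Receivers: (42 + 10.5)/(42 + 21) = 0.83. All cases at 40% receipt: (42 + 4.2)/(42 + 8.4) = 0.92.
- Given in days 1–21: the means are 31.5 and 10.5. Receivers: 73.5/52.5 = 1.40. All cases: 54.6/46.2 = 1.18.
- Non-receivers: 1.00 in both.

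The receiver stratum is therefore further from 1 than the unstratified estimate. The non-receiver stratum is clean, but only without deferral.

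**Step 4: the time-varying term under deferral.** Neither vaccine has an effect, 40% are planned, and the ABRYSVO IRR is simulated from a conditional Poisson model with an other-vaccine term:

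| Planned days | Other-vaccine window | 50% cancelled | 100% cancelled |
|---|---|---|---|
| 1–84 | 42 days | 1.03 | (not tabulated) |
| 43–84 | 42 days | 1.12 | 1.25 |
| 29–56 | 42 days | 1.18 | 1.36 |
| 1–84 | 84 days | 1.12 | 1.24 |

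The unstratified SCRI without the term stays at 1.00–1.01. For comparison, the strata for days 43–84 are: receivers (1 − c)/(1 − 0.5c) = 0.67 at c = 0.5 and 0 at c = 1; non-receivers 0.80/0.70 = 1.14 and 1.00/0.80 = 1.25. Without deferral the time-varying term is unbiased. In every scenario examined it was no further from 1 than the worse stratum.

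**The case against.** The strongest reply is that nothing here is fixed. Section 9.7.4 lists these analyses as feasible options, leaves details to the SAP, and the SAP could define strata by timing. The time-varying model is already allowed. That limits the weight of the point but does not remove it: the stratification is the only SCRI remedy 9.7.4 names for vaccines given during follow-up, and both sections describe it by receipt over the interval.

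A reader might infer that the split is bound to occur. It is not. It needs the event to change later vaccination, which the protocol neither states nor quantifies for other vaccines; its remark about deferral concerns ABRYSVO. Short deferral gives little split, and the signs reverse if events increase vaccination.

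A reader might also infer that vaccines given shortly before index would go unexamined. Section 9.9 does not support that: it names them as a separate concern and offers the exclusion unconditionally. What stands is that the two sections differ on when the exclusion applies.

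Finally, the replacement shares a weakness. A time-varying term also assumes the event does not affect later exposure, and step 4 shows that failure reaching the ABRYSVO IRR as well as the other-vaccine coefficient. This objection stands in full and shapes the fix.

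**Conclusion.** The point holds in conditional form. If events reduce later vaccination, the proposed strata turn a null into an IRR below 1 among receivers, which is the larger distortion, and modestly above 1 among non-receivers: 0.87/1.08 at 25% cancellation and 0.71/1.15 at 50%. If the other vaccine itself carries risk, the receiver stratum misleads even without deferral (0.83 or 1.40 in the two timings shown). These sizes rest on equal 42-day intervals, 40% planned vaccination, the stated timings and, for the last pair, an assumed doubling of risk for 42 days.

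The stronger reading, that the study's safety results are biased, is not supported. The comparative cohort and the unstratified SCRI do not use this split. The consequence is confined to an optional sensitivity analysis, but a better one costs almost nothing.

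**What to change.** In 9.7.4 and 9.9, replace the stratification with the unstratified conditional Poisson model plus a time-varying indicator for a prespecified window after any other vaccine, as 9.7.3.2 permits. Report it beside the SCRI without that term. If strata are wanted, define them only by information fixed at index, such as another vaccine on the ABRYSVO date or in the 30 or 45 days before it.

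State the limitation with it: under event-dependent deferral the other-vaccine coefficient is distorted and should not be interpreted, and the ABRYSVO IRR can be biased upward, to about 1.1–1.4 when other vaccines cluster around the end of the risk interval or in the control interval. The two estimates should be read together.

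Reconcile 9.7.4 with 9.9 so that the 30/45-day pre-index exclusion does not depend on imbalance after index.

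The cost is protocol and SAP wording, one model term and one prespecified window length. The planned descriptive check already needs the vaccination dates.
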